7.1 Setting and Target Population

The study population will include all patients that received a CCTA for symptoms suggestive of CAD at a participating institute, 12 months prior to the institutes first FFRCT study and up to 24 months

MRC

 $\mathcal{L}_{\mathcal{L}}$

FISH&CHIPS

following (total study period up to 36 months). The timeframe of study recruitment is dependent upon the starting time of each centre in the ITP programme. Centres that had a later start date (onboarding) will have a shorter recruitment period, with a minimum of 12 months. These centres represent the 'real-world' NHS hospitals that are a mixture of secondary and tertiary referral centres (not dedicated academic or research sites) with clinical experience in CCTA who have met the minimum quality standards set out by NHS England. Thus, the study population represents a true reflection of the current CCTA practice in the national population, reducing the potential effect of selection bias seen in many RCT's.

A study population of 85,292 patients received either CCTA analysis alone (standard of care group, n=75,361) or CCTA and Heartflow FFRCT analysis (FFRCT group, n=9,799) during the two years of the new technology being available to each site. The total study population over the 36 months is likely to be over 100,000.

7.2 Inclusion Criteria

7.2.1 Site eligibility:

- Sites within NHS England with a FFRCT ITP programme commencing between April 1st 2018-March 31st 2020
- Sites must have performed a minimum number of ≥50 FFRCT within 1 year of their programme commencing

7.2.2 Individual eligibility:

- Age ≥18 years
- CCTA for the assessment of coronary artery disease (CAD)

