Liverpool Centre for Cardiovascular Science

The FISH&CHIPS Protocol

FFRCT In Stable Heart disease and Coronary Computed Tomography Angiography Helps Improve Patient care and Societal costs

Study Objective	The primary objective of FISH and CHIPS is to identify differences in health- related events, time to diagnosis and overall healthcare costs of a stable chest pain population undergoing Coronary Computed Tomography Angiography (CCTA) and Fractional Flow Reserve (FFR _{CT}), compared to a previous 'standard of care' diagnostic chest pain pathway of CCTA and non- invasive functional testing.	
Study Design	This is a multi-centre, retrospective, observational analytic cohort study design. The study will utilise the electronic health record (EHR) data already collected by NHS England on all patients that underwent a CCTA for the assessment of coronary artery disease over a 2-year period (April 2017-April 2019). All patients were treated in accordance with the latest NICE clinical guidance (CG 95 2016). Healthcare data will be collected from 6 months prior to and 12 months following the index CCTA. Hospital admissions data collected will include inpatient hospital admissions, outpatient visits, cardiovascular diagnostic tests and procedures. All subsequent clinical events including myocardial infarction and all-cause death will be measured as clinical outcomes. Costs are determined from the NHS national tariff system.	
Study Principal	[name]	
Investigator	Liverpool Heart and Chest Hospital and the University of Liverpool,	
	[name],	
	Liverpool,	
	[name]	
	United Kingdom	
Sponsor	Liverpool Heart and Chest Hospital,	
	[name],	
	Liverpool,	
	[name]	
	United Kingdom	
FISH	& CHIPS MRC Medical Research Council	

RESEARCH REFERENCE NUMBERS

IRAS Number:	285996
ISRCTN Number / Clinical trials.gov Number:	
FUNDERS Number:	MR/T024933/1

Medical MRC

Investigator Protocol Signature Page

The undersigned confirm that the following protocol has been agreed and accepted and that the Chief Investigator agrees to conduct the trial in compliance with the approved protocol and will adhere to the principles outlined in the Medicines for Human Use (Clinical Trials) Regulations 2004 (SI 2004/1031), amended regulations (SI 2006/1928) and any subsequent amendments of the clinical trial regulations, GCP guidelines, the Sponsor's (and any other relevant) SOPs, and other regulatory requirements as amended.

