3.1 Professional Summary

Protocol Title	FFRCT In Stable Heart disease & CCTA Helps
	Improve Patient care and Spending
Investigation strategy	CCTA plus FFRCT reduces healthcare resource
	utilization and costs compared to a CCTA
	strategy alone.
Study Principal Investigator	[name]
Academic Research Organization	Liverpool Centre for Cardiovascular Science
	(LCCS), Liverpool Heart and Chest Hospital,
•	Liverpool, UK
Sponsor	The University of Liverpool
Participants and Study sites	Approximately 100,000 patients from 25 sites
	who received a CCTA for the assessment of CAD
	in NHS England.
Study Planned Duration	36 months
Primary study objective	To determine whether a CCTA and FFRCT
	diagnostic pathway reduces health-related
	events, time to diagnosis and overall healthcare
	costs compared to a 'standard of care' CCTA
	diagnostic chest pain pathway.
Primary hypothesis	The addition of FFRCT into a CCTA diagnostic
	pathway will be safe with no difference in major
	adverse cardiovascular event rates or death
	whilst reducing the time to diagnosis, result in
	fewer downstream tests and reduce overall costs
	to the healthcare system.
Population	Chest pain patients with suspected stable
	coronary artery disease being clinically
	investigated with a CCTA in England.
Study Design and Methods	A pragmatic 'real world' multi-centre,
	retrospective, observational analytic cohort
	study design. All patients receiving a CCTA at
	institutions utilising FFRCT as part of NHS
	England's Innovation and Technology Payment
	(ITP) programme. Participants will be recruited
	from 1 year pre-ITP and the 2 years of the ITP
	programme. Patients will be followed up at a
	minimum of 24-months post CCTA for the pre-
Duine and Findle sint	defined primary and secondary endpoints.
Primary Endpoint	Primary and secondary outcomes measured:
	1. MI event rate, hospitalization for
	acute coronary syndrome, MI deaths
	and all-cause death.
	2. Downstream testing: numbers of

MRC Researc

	 non-invasive functional tests, and invasive coronary angiograms without revascularisation performed following the index FFRCT. 3. Cost analysis: Total cost to the NHS of the index test and all downstream investigations and hospital admissions. 	
Secondary Endpoint	 Time to diagnosis- Trust Referral to Treatment (RTT) time. 	
	 Qualitative assessment of the impact of the FFRCT health technology 	
Study follow up	Participants will be followed up to a minimum of 24 months	

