5.1 Primary objective

The study aims to identify differences in health-related events, time to diagnosis and overall costs in a clinical population undergoing CCTA and FFR_{CT} for symptoms suggestive of stable CAD, compared to a previous 'standard of care' diagnostic chest pain pathway.

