5.4.2 Imaging biomarkers

Using the list of CCTA originally provided by the sites, the participating centres PACS teams will send the anonymised CCTA datasets to the CTU data storage for future linkage to the outcome data provided by NHS Digital. This process will ensure that anonymity is preserved while providing for a valuable resource in terms of a large database of anonymised imaging datasets with outcome data. There will also be the opportunity to repeat the data capture from NHS Digital in future years to establish medium and long-term outcomes. The purpose of creating this repository of anonymised outcome and imaging data is to allow for future research projects into image analysis of CTA including deep learning algorithms, radiomics analysis, and biomechanical modelling of coronary arteries all with the goal to improving future risk stratification to better target therapeutic interventions.

6 Study Design

This is a multi-centre, retrospective, observational analytic cohort study design.

This pragmatic 'real-world' trial, is designed to utilise big data to answer practical health questions and determine clinical outcomes in a timely fashion. Randomized clinical trials (RCT's) in comparative effectiveness research (CER) have been considered the gold standard. These are however, subject to several problems, including cost, patient selection bias and slow translation of knowledge into practice. (Angus, 2015) This study design removes any patient treatment heterogeneity effect seen in RCT's by assessing the impact of a new intervention on a whole population. (Longford, 1999) by utilising the electronic health record (EHR) data already collected by the NHS. This trial will thus represent a true assessment of the effectiveness of a new health technology on a population basis in the current NHS system and will enable the rapid translation of research into clinical and health care policy decisions.

Participants will include all individuals who had a CCTA performed at an institute participating in the NHSE FFRCT ITP during 2018-2020. All CCTA 12 months prior to and up to 24 months following the

FISH&CHIPS

Medical Research Council

start of a FFRCT programme (total study period 36 months) will be assessed. The cohort from this population that received an FFRCT will be separately identified, with linkage to the NHS digital data outcomes. HeartFlow will provide FFRCT-specific data.

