7.3 Exclusion Criteria

- Age <18 years
- Coronary artery calcium scoring alone
- CCTA in addition to a second CT investigation for a non-coronary indication (CT TAVI, CT aorta)

mam

Liverpool Centre for Cardiovascular Science

- Previous CCTA within 6 months
- Prior CABG / MI
- Entry into a separate FFRCT research study during the study timeframe

[figure not shown]

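### The eligibility rules do not require a stable presentation, so scans done during an emergency admission qualify and later events in that admission can count as outcomes

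*Protocol*

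**What the plan says.** The target population is stable in three places. The cover synopsis speaks of "overall healthcare costs of a stable chest pain population". The Population row of section 3.1 begins "Chest pain patients with suspected stable" and continues with coronary artery disease. Section 5.1 restricts the objective to a clinical population tested "for symptoms suggestive of stable CAD".

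The rules that select patients are wider:

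- Section 6: "Participants will include all individuals who had a CCTA performed at an institute participating in the NHSE FFRCT ITP".
- Section 7.1: "all patients that received a CCTA for symptoms suggestive of CAD at a participating institute". Symptoms are required, but stability is not.
- Section 7.2.2: age 18 or over, and "CCTA for the assessment of coronary artery disease (CAD".
- Section 7.3 excludes prior CABG or MI, "Previous CCTA within 6 months", calcium scoring alone, CT combined with a non-coronary scan, and entry into another FFRCT study. It names neither acute or inpatient presentation nor prior PCI.

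On outcomes, the safety endpoints in section 5.3 are MI, hospitalisation for acute coronary syndrome, and mortality. The MACE composite in section 8.2 is all-cause death, MI and invasive angiography without revascularisation, with Kaplan-Meier time running from the CCTA. Section 6 costs all hospital attendances, and section 8.2 compares total pathway cost at 12 months.

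**The concern.** This is a retrospective record study without consent. No clinician judges at enrolment whether a patient belongs, so the written criteria are the only patient filter. If they are broader than the objective, the cohort analysed is broader than the population the conclusions describe.

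A scan done during an emergency spell causes a specific difficulty. The illness that led to the admission was under way before time zero, but its investigation and coding may continue afterwards. Part of the presenting episode can then be recorded as a consequence of the diagnostic pathway. This touches three of the primary endpoints in section 5.3: safety, downstream testing and cost.

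It also touches the plan in section 8.1 to compare observed with expected events as a check of safety. One benchmark there is a registry study whose title in the reference list describes stable individuals. A cohort containing acute presentations is not like-for-like with it, even if acute patients are balanced between the two testing groups.

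**Working it through.** No stated figure depends on the criterion, so there is nothing to reproduce. The check is a comparison of the sections, followed by a short illustration under assumed inputs.

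**Step 1: is an emergency-spell CCTA eligible?** Take an adult admitted with acute chest pain, with no earlier MI or CABG, who has a CCTA during the stay.

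| Section | Requirement | Met? |
|---|---|---|
| 6 | CCTA at a participating site | Yes |
| 7.1 | Symptoms suggestive of CAD | Yes |
| 7.2.2 | Adult; CCTA to assess CAD | Yes |
| 7.3 | None of the listed exclusions | Yes |
| Cover, 3.1, 5.1 | Stable or suspected stable disease | No |

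The selection rules admit a patient whom the objective does not describe. Section 7.4 uses the six months before the scan to look for pathway crossover and prior testing, not to remove acute presentations.

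**Step 2: what can then be counted?**

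- The admission itself began before the scan. With the clock starting at the CCTA, it falls outside the count on a plain reading.
- An angiogram without revascularisation later in the spell is dated after the scan. It falls within the section 8.2 composite and is the type of test that the downstream-testing endpoint in 5.3 counts.
- An MI coded after the scan in the same spell falls within both the 8.2 composite and the 5.3 safety endpoint.
- The spell is a hospital attendance. Nothing in sections 5.3, 6 or 8.2 separates its cost from pathway cost.

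**Step 3: prior PCI.** A patient with an earlier stent and no MI or CABG passes 7.3. Section 3.1 describes suspected disease, which sits awkwardly with a patient already treated for it. The protocol does not say whether this is intended.

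**Step 4: illustration only.** Let b be the one-year event rate without the problem, s the share of scans done in an emergency spell, and q the share of those with a same-spell event that is counted. Then:

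observed rate = b + s × q × (1 − b)

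Section 8.1 quotes 1.16% at one year for an FFRCT registry, used here as b. Both s and q are assumptions, because the protocol gives neither.

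| s | q = 0.10 | q = 0.25 | q = 1 |
|---|---|---|---|
| 1% | 1.26% | 1.41% | 2.15% |
| 5% | 1.65% | 2.40% | 6.10% |

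For example, with s = 1% and q = 0.25: 1.16% + 0.01 × 0.25 × 98.84% = 1.16% + 0.25% = 1.41%.

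These are rates within one group, not a bias between groups. With no true effect and the same s and q in both groups, the ratio is 1. With q = 0.25 and shares of 2% and 1%, the rates are 1.654% and 1.407%. The ratio of FFRCT to standard care is then 1.407/1.654 = 0.85 if the larger share is in standard care, and 1.654/1.407 = 1.18 if it is in the FFRCT group. The protocol does not indicate which, if either, applies.

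The 1.16% is an imperfect reference. The protocol does not define the registry's events, and the 8.2 composite also includes angiography without revascularisation. If the true base rate is higher, the proportional effect is smaller.

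**The case against.** The strongest reply is that the target population is fixed elsewhere: 3.1 and 5.1 say stable, the cover says patients were managed under the national chest pain guidance, and 7.2.2 is a terse list beneath that statement. The target is indeed stated, so the defect is a mismatch and not an absence. The reply does not close the gap, because a data extraction follows the criteria and these contain no stability condition. The guidance, as titled in the reference list, concerns chest pain of recent onset, which is not limited to stable pain.

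A second reply is that handling of a spell open at time zero may sit in the statistical analysis plan, which is not at hand. That is fair for the event-counting rule. It does not answer the eligibility mismatch, which belongs to the protocol.

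A third is that the prior-MI exclusion may already remove inpatients whose infarction precedes the scan. This narrows the affected group, mainly to unstable angina or undifferentiated acute chest pain, but does not empty it. ACS hospitalisation is also absent from the 8.2 composite, so an index ACS admission does not reach that composite unless an MI code or an angiogram without revascularisation follows the scan.

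Several stronger readings are tempting but unsupported:

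- That patients without symptoms are admitted: 7.1 requires symptoms.
- That the study must exclude all known CAD: absence of prior CAD appears only as background in 4.1, and prior CABG and MI are excluded. Leaving PCI out may be deliberate in a pragmatic study.
- That emergency patients have no referral-to-treatment start: section 6 says these data are collected for each patient.
- That acute patients sit mostly in the CCTA-alone or pre-FFRCT group and make FFRCT look safer and cheaper: no section says so.

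**Conclusion.** The point holds as a mismatch between the stated population and the operative eligibility rules. As written, a CCTA done during an emergency admission is eligible, and later MI codes, angiograms without revascularisation and costs from that spell can enter the endpoints. Whether such patients are in fact present, how many there are, and whether their share differs between groups cannot be learned from the protocol. The size and direction of any bias are therefore unknown. The illustration shows only that, with event rates near 1%, a small share could be visible. It rests on assumed values of s and q and should not be cited as an estimate. The conclusion assumes that no unseen analysis rule already removes events from spells open at the scan.

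**What to change.** Align 7.2.2 with the objective by requiring CCTA for suspected stable CAD, and bring sections 6 and 7.1 into line. In the records, implement this by excluding scans whose date falls within an emergency admission (HES APC) or A&E attendance (ECDS, HES AE). Say how same-day cases are ordered, since an attendance that follows the scan may be a genuine outcome.

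State that diagnoses and procedures from a spell already open on the CCTA date are not outcome events, and say how that spell's cost is treated. Show the all-comer cohort as a sensitivity analysis.

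In 7.3, state whether prior PCI is excluded alongside prior CABG and MI; if it is not, analyse those patients as a subgroup. If an all-comer cohort is what the sponsor wants, the objective and population statements should change instead.

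The cost is an amendment to the eligibility text and filters on data already requested, since section 6 lists dates and methods of admission. The prior-PCI filter needs history of the kind that the CABG and MI exclusion already requires. The drawback is a loss of patients, of a size the protocol does not give, from a cohort of about 100,000.

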7.3 Exclusion Criteria

- Age <18 years
- Coronary artery calcium scoring alone
- CCTA in addition to a second CT investigation for a non-coronary indication (CT TAVI, CT aorta)

mam

Liverpool Centre for Cardiovascular Science

- Previous CCTA within 6 months
- Prior CABG / MI
- Entry into a separate FFRCT research study during the study timeframe

[figure not shown]

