7.4 Follow up

Patient data will be collected up to a minimum of 24 months post-CCTA. Clinical data will also be analysed for the 6 months pre-CCTA to ensure no cross over between diagnostic pathways and prior testing (including CCTA) within 6 months (Figure 1).

Longitudinal long-term follow-up (>2 years) at 5 and 10 years would be feasible and cost effective using the same methodology of HES downloads and data analysis. This would provide a true long-term perspective of health care resource use in a stable angina population

Figure 1 Study Design Overview

8 Statistical Methodology

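### The exclusion for entering another FFRCT study is not anchored to the index CCTA, so patients can be removed for something that happens after it

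*Protocol*

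**What the plan says.** Protocol section 7.3 lists as an exclusion "Entry into a separate FFRCT research study during the study timeframe". It does not say whether entry must come before, at or after the index CCTA. Other items in the same list look back from the index scan, for example "Previous CCTA within 6 months" and the exclusion for earlier bypass surgery or infarction.

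The readable text does not define the study timeframe. It offers several candidates:

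- Section 7.1 takes scans from "12 months prior to the institutes first FFRCT study and up to 24 months" after it, and calls this a "total study period up to 36 months".
- Section 6 gives the period without the qualifier: "start of a FFRCT programme (total study period 36 months) will be assessed".
- Section 7.1 also says "Centres that had a later start date (onboarding) will have a shorter recruitment period, with a minimum of 12 months".
- Section 7.4 adds follow-up: "Patient data will be collected up to a minimum of 24 months post-CCTA".
- The front-page synopsis gives a two-year period, April 2017 to April 2019, with 12 months of data after the index scan.

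The protocol gives no number of patients removed under this rule.

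**The concern.** The study is retrospective, so eligibility is applied with each patient's later history already on file. Read literally, the rule uses that history. A patient scanned under ordinary care in month 3 who joins an FFRCT study in month 30 leaves the cohort with all data. A similar patient who dies in month 20 stays. Only someone who is alive can be removed in this way, and the person removed is likely to be under renewed investigation.

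This reaches the endpoints directly. Death is part of the safety endpoint in section 5.3 and of the composite in section 8.2. That composite also counts invasive angiography without revascularisation, and repeat testing drives the downstream-test and cost endpoints.

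The chance of removal also depends on when the patient was scanned. Earlier scans leave more of the window still to run, and the earliest scans are those from the pre-FFRCT year. The stated objective compares the FFRCT pathway with an earlier standard of care, so the two sides of that comparison can be filtered unequally. Eligibility is settled in the protocol, and later modelling cannot restore patients left out of the extract.

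**Working it through.** **Inputs.** From section 7.1: 12 months before and up to 24 months after the site's first FFRCT; 75,361 CCTA-alone and 9,799 FFRCT patients in the two FFRCT years; 85,292 as the stated total for those years; a likely overall total above 100,000. From section 8.1: a 1.16% one-year event rate in an FFRCT registry. Assumed, because the protocol does not give them: even accrual within each period, and a constant rate of entry into other studies.

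**The plan's own figure.** 12 + 24 = 36 months, as stated.

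**Post-index time in the window.** Let p be the months after FFRCT start, f any follow-up added to the timeframe, and T = 12 + p + f. With even accrual, the mean post-index time is T − 6 for pre-FFRCT scans and T − (12 + p/2) for FFRCT-era scans.

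| Reading of the timeframe | Pre-FFRCT (months) | FFRCT era (months) | Ratio |
|---|---|---|---|
| 12 + 24 | 36 − 6 = 30 | 36 − 24 = 12 | 2.5 |
| 12 + 18 (later start) | 30 − 6 = 24 | 30 − 21 = 9 | 2.67 |
| 12 + 12 (later start) | 24 − 6 = 18 | 24 − 18 = 6 | 3.0 |
| 12 + 24, capped at 24 months per patient | 24 | 12 | 2.0 |
| 12 + 24, plus 12 months of follow-up | 48 − 6 = 42 | 48 − 24 = 24 | 1.75 |
| 12 + 24, plus 24 months of follow-up | 60 − 6 = 54 | 60 − 24 = 36 | 1.5 |
| 12 + 12, plus 24 months of follow-up | 48 − 6 = 42 | 48 − 18 = 30 | 1.4 |

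A simulation of one million scan dates per period gave 30.00 and 12.00 months for the first row. If accrual in the FFRCT years is uneven, so that mean remaining time is 8 to 14 months, the first-row ratio runs from 30/8 = 3.75 to 30/14 = 2.14.

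**Other comparators.**

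- CCTA-alone patients scanned in the FFRCT years against FFRCT patients: 12/12, about 1.0 if both accrue alike.
- All CCTA-alone patients pooled, with a pre-FFRCT year of 100,000 − 85,292 = 14,708: (14,708 × 30 + 75,361 × 12) / 90,069 = 14.94 months, and 14.94/12 = 1.24.
- The same with a pre-FFRCT year of 85,292/2 = 42,646: ratio 1.54.

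**Illustrative effect.** Take the first row, an assumed annual entry rate, a true risk of 1.16% on both sides, and no event among those removed.

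- At 1% a year, 2.5% of pre-FFRCT and 1% of FFRCT-era patients go: 1.16/0.975 = 1.19% against 1.16/0.99 = 1.17%, a gap of about 0.02 points.
- At 5% a year, 12.5% and 5% go: 1.16/0.875 = 1.33% against 1.16/0.95 = 1.22%, a gap of about 0.10 points.

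With 14,708 and 85,292 patients, these rates imply about 368 + 853 = 1,221 and 1,839 + 4,265 = 6,104 removals. The second is 62% of the FFRCT group (6,104/9,799), so 5% is an extreme case.

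**The case against.** The best defence is that the item is only loosely worded. The other exclusions concern status at or before the index scan, and this one may be meant simply to keep research-driven FFRCT out of a routine-care cohort. Figure 1, which could not be read here, may show the timeframe. That is a fair account of the likely intention, but the text as it stands allows removal for later entry, and nothing in the readable sections limits it.

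A reader might infer that controls are exposed to the rule 2.5 times as long, as a fact of the design. The documents do not support that. The figure needs the full 36-month window, even accrual, a count of post-index time only, and a contrast of pre-FFRCT with FFRCT-era scans. Section 7.1 attaches its standard-of-care label to CCTA-alone patients scanned in the FFRCT years, and section 8.2 compares time to diagnosis by test received. For that concurrent contrast the ratio is about 1.0. If the timeframe meant the same fixed follow-up for every patient, the imbalance would also vanish, though selection on later events would remain.

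A reader might also infer that the rule favours a finding that FFRCT is safe. That is not established. Removing survivors raises comparator mortality. But re-investigated patients may already have had angiography without revascularisation, which counts in the section 8.2 composite, and removing them lowers the comparator's rate. It also lowers its test counts and costs. The illustrative event rates above show one direction only because they assume that those removed had no event.

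**Conclusion.** The point holds as a defect of wording that permits selection on the future. The exclusion is not anchored at the index CCTA, the timeframe is undefined, and a routine-care patient can be removed for a later event that only survivors can have.

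Pre-FFRCT patients have more post-index time at risk under each site-window reading tried: about 2.5 times in the full-window, even-accrual case and roughly 1.5 to 3.0 otherwise, with one combination of a short window and long follow-up at 1.4. This does not extend to the concurrent CCTA-alone group.

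The direction of bias differs by endpoint, and the net effect on the composite is unknown. The size cannot be computed from the protocol and is small if entry is rare. The 132-patient gap in section 7.1 (75,361 + 9,799 = 85,160 against 85,292) is unexplained and should not be attributed to this rule. This is a cheap improvement to make, not a threat to the study's main conclusions on present evidence.

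**What to change.** Reword the item in section 7.3 to: *Index CCTA or its FFRCT performed as part of, or while enrolled in, a separate FFRCT research study*. This no longer relies on an undefined timeframe, and it brings post-index exposure to the rule to zero in both eras.

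Keep patients who enter such a study after the index CCTA, with all follow-up, in the group fixed at index. Report their number per group, and run a sensitivity analysis that censors them at entry.

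The cost is one line of protocol text and an entry date for each identified participant. The protocol names no source for enrolment in other studies, so whatever source is used must supply that date. The downside is that a few retained patients may carry research-driven tests into the test-count and cost endpoints; the count and the sensitivity analysis show whether that matters.
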